7 SAFETY ASSESSMENT

7.1 Safety Measures

It is the responsibility of the Principal Investigator to oversee the safety of the patients and to report all AEs/SAEs that are observed or reported during the study, regardless of relationship to study drug or clinical significance.

All patients taking study drug will be subject to DLT assessments, but patients in Phase 2 are unlikely to have DLTs, given that the dose of drug they are taking, is below the MTD determined in Phase 1.

The investigator together with the Sponsor's Medical Monitor will review all safety information per patient at each dose-finding meeting.

Safety data will also be reviewed on a regular basis by Spectrum's study monitoring team, which includes a Clinical Research Associate (CRA), Clinical Trial Manager (CTM), Medical Monitor, and other personnel from the company or its designee.

Adverse events will be characterized by intensity (severity), causality, and seriousness by the Investigator based on the regulatory definitions included below.

This study will utilize the National Cancer Institute (NCI) Common Terminology Criteria for Adverse Events (CTCAE) Scale Version 5.0 for AE grading.

7.2 Adverse Events

An AE is defined as any untoward medical occurrence in a patient or clinical investigation patient, temporally associated with the use of a medicinal product, whether or not considered related to the medicinal product. Therefore, an AE can be any unfavorable and unintended sign (including an abnormal laboratory finding), symptom, or disease (new or exacerbated) temporally associated with the use of a medicinal product. A treatment-emergent AE (TEAE) is any AE that occurs from the first dose of study treatment until 35 (± 5) days after the last dose of study treatment.

The study will record all AEs according to the information in [Section 7.3](#).

Examples of AEs **include**:

- Exacerbation of a chronic or intermittent pre-existing condition including either an increase in frequency and/or intensity of the condition.
- New conditions detected or diagnosed after investigational product administration.
- Signs, symptoms, or the clinical sequelae of a suspected drug interaction.
- Signs, symptoms, or the clinical sequelae of a suspected overdose of either investigational product or a concurrent medication.
- AEs may include pre-treatment or post-treatment events that occur as a result of protocol-mandated procedures, ie, invasive procedures.

Abnormal laboratory results are to be recorded as AEs, if any of the following conditions are met:

- The abnormal laboratory value leads to a therapeutic intervention.

- The abnormal laboratory value is considered to be clinically significant by the Investigator.
- The abnormal laboratory value is predefined as an AE in the protocol or in another document communicated to the Investigator by Spectrum or designee.

Examples of events that **do not** constitute AEs include:

- Medical or surgical procedures (eg, endoscopy, appendectomy); the condition that leads to the procedure is an AE.
- Situations where an untoward medical occurrence does not occur (eg, social and/or convenience admission to a hospital).
- Anticipated day-to-day fluctuations of pre-existing disease(s) or condition(s) present or detected at the start of the study that do not worsen.
- Planned and prescheduled hospitalizations and procedures.
- Progressive disease and death due to disease progression.

The adverse events of special interest identified with pozotinib treatment in this study include diarrhea, skin rash, oral cavity mucositis/stomatitis, fatigue, and vomiting/nausea.

7.3 Guidelines for Recording and Attribution Scoring of Adverse Events

Timely and complete reporting of all AEs is required for all patients. Monitoring and documentation of all AEs allows for identification of potential study-drug or dose-related AEs, and for adherence to regulatory requirements. Please refer to the CRF Completion Guidelines located in the study binder for detailed instructions for AE reporting.

7.3.1 Recording of Adverse Events

All AEs that occur from the first dose of study treatment through 35 (± 5) days after the last dose of study treatment is administered are to be recorded on the AE CRF. From the time the study Informed Consent is signed through the first dose of study drug administration, all SAEs are to be recorded. In addition, SAEs that occur after 35 (± 5) days after the last dose of study treatment where a causal relationship with the study drug is suspected will also be recorded on the AE CRF.

The resolution of all AEs must be routinely recorded and be reconciled at the end of the study. The following conventions will be followed when patient completes or discontinues from the study:

- If a patient dies, the date of death should be the date of AE stop for all ongoing AEs at the time of death.
- The outcome of the AE is to be followed for 35 (± 5) days from the date of discontinuation or until the AE has returned to Grade ≤ 1 . The status of the AE and the date of last contact with the patient will be captured. If the AE has not returned to Grade ≤ 1 by the end of the study, the AE stop date should be left as ongoing.

All AEs will be classified by CTCAE Grade ([Section 7.3.2](#)), relationship to study drug ([Section 7.5](#)), and as serious or nonserious ([Section 7.7](#)) by the Investigator.

7.3.2 Grading of Adverse Events

This study will utilize the NCI CTCAE Scale, Version 5.0 for AE grading.

7.4 Follow-up of Adverse Events

All AEs and significant abnormal laboratory values are to be followed up in accordance with the International Conference on Harmonization (ICH) Good Clinical Practice (GCP) guidelines, and other applicable regulatory requirements (eg, United States [US] Code of Federal Regulations [CFR]).

7.5 Relationship

The Investigator must make a causality assessment and document their opinion as to the relationship of all AEs and SAEs to study treatment ([Table 4](#)).

Table 4 Investigator Assessment of Adverse Event Causality

Relationship	Description
Not Related	The event is clearly related to factors other than study treatment, such as the patient's clinical state, therapeutic interventions, or concomitant medications administered to the patient.
Unlikely Related	The temporal association, patient history and/or circumstances are such that the study drug or treatment is not likely to have had an association with observed event.
Possibly Related	The event follows a reasonable temporal sequence from the time of study treatment administration, and/or follows a known response pattern to study treatment, but could have been produced by other factors, such as the patient's clinical state, therapeutic interventions, or concomitant medications administered to the patient.
Probably Related	The event follows a reasonable temporal sequence from the time of study treatment administration, and follows a known response pattern to study treatment, and cannot be reasonably explained by other factors, such as the patient's clinical state, therapeutic interventions, or concomitant medications administered to the patient.
Definitely Related	The event follows a reasonable temporal sequence from the time of study treatment administration, and follows a known response pattern to study treatment, and cannot be reasonably explained by other factors, such as the patient's clinical state, therapeutic interventions, or concomitant medications administered to the patient. In addition, the event either occurs immediately following study treatment administration, improves on stopping study treatment, reappears on repeat exposure, or there is a positive reaction at the application site.

7.6 Expectedness

For investigational drugs, an AE is judged “expected” if its description agrees in nature and severity with the description of AEs previously noted with the study drug as detailed in the current Investigator’s Brochure. An “unexpected” AE is one for which the specificity or severity is neither consistent with the current Investigator’s Brochure nor the risk information described in the general investigational plan. The Sponsor will be responsible for assessing the expectedness of AEs.

The most common AEs associated with pozotinib treatment include:

- Diarrhea
- Rash
- Stomatitis
- Fatigue
- Vomiting
- Decreased Appetite
- Dry Skin
- Nausea

7.7 Serious Adverse Events

In the interest of patient care and to allow Spectrum to fulfill all regulatory requirements, any SAE, regardless of causal relationship to study treatment, is to be reported to the Sponsor within 24 hours of knowledge of the event. SAEs are defined (21 CFR 312.32, ICH of Technical Requirements for Registration of Pharmaceuticals for Human Use E2A Guideline) as those AEs that meet any of the following criteria:

- Results in death.
- Is life-threatening: ie, any event that, in the opinion of the Investigator, poses an immediate risk of death from that event.
- Requires inpatient hospitalization or prolongation of existing hospitalization (excluding hospitalizations for study therapy, disease-related procedures, or placement of an indwelling catheter, unless associated with other SAEs).
- Results in a persistent or significant disability/incapacity.
- Results in a congenital anomaly/birth defect.
- Includes important medical events that may not be immediately life threatening or result in death or hospitalization but may jeopardize the patient or may require intervention to prevent one of the outcomes listed in this definition.

Adverse events that do not meet any of the above criteria for serious should be regarded as non-serious.

7.7.1 Serious Adverse Event Reporting

From the time the study Informed Consent is signed through the first dose of study drug administration, all SAEs are to be recorded. All SAEs that occur from the first dose of study drug administration through 35 (± 5) days after the last dose of study treatment and SAEs that occur after 35 (± 5) days after the last dose of study treatment where a causal relationship with the study drug is suspected are to be reported to Spectrum within 24 hours of knowledge of the event.

SAEs are to be reported and the serious adverse event report (SAER) faxed or e-mailed within 24 hours of knowledge of the event to the study Sponsor:

Spectrum Pharmaceuticals, Inc.
Primary Contact: Pharmacovigilance Department
Fax: + 1 [contact]
E-mail: [contact]

Spectrum may request additional information from the Principal Investigator to ensure the timely completion of accurate safety reports. Safety data that are critical to the reportability of an SAE, such as causality assessment and serious criteria, should be included in the initial faxed or e-mailed SAER. If omitted, a timely response to drug safety data queries received from Spectrum or designee is expected.

The Investigator is to take all appropriate therapeutic measures necessary for resolution of the SAE. Any medications necessary for treatment of the SAE are to be recorded in the concomitant medication section of the patient's CRF.

SAEs that are study-treatment related will be followed until resolution or until they have returned to Grade 1, whichever is longer, or until it is determined that the outcome will not change with further follow-up.

Additionally, the SAE is to be entered in the AE section of the CRF. Follow-up SAERs need to be submitted to Spectrum within 24 hours, once additional information regarding the event becomes available (eg, final diagnosis is made, laboratory or test results, event course, outcome, etc).

The Sponsor or its designee will be responsible for reporting SAEs to the regulatory authorities in accordance with applicable expedited reporting regulatory guidelines. The Principal Investigator is responsible for submitting SAEs to his/her site's Institutional Review Board (IRB)/Ethics Committee (EC) through the head of the study site. Copies of each SAER, and documentation of IRB/EC notification and acknowledgement of receipt, will be kept in the Site's Regulatory Binder.

In addition, all deaths that occur on study will be reported on a death CRF page.

7.7.2 Exclusions to Serious Adverse Event Reporting Requirements

The following are not considered SAEs:

- Situations where an untoward medical occurrence did not occur (eg, social and/or convenience admission to a hospital, hospitalization for diagnostic tests such as CT scans).
- Anticipated day-to-day fluctuations of pre-existing disease(s) or condition(s) present or detected prior to first study treatment administration that do not worsen.
- Planned and prescheduled hospitalizations and procedures.
- Progressive disease and death due to disease progression.

7.8 Reproductive Risks

No adequate and well-controlled studies of pozotinib have been conducted in pregnant women. The effect of pozotinib on fertility and fetal development have not been studied in pregnant women. Pozotinib is not recommended for use during pregnancy.

Any pregnancy involving a study patient or a patient's partner that occur from the first dose of study treatment through 35 (± 5) days after the last dose of study treatment is to be reported to the Sponsor within 24 hours after the Investigator has gained knowledge of the event via fax or e-mail (see contact information in **Section 7.7.1**). Pregnancies should be followed up until outcome and follow-up information regarding the outcome of the pregnancy should be faxed or e-mailed to Spectrum's Pharmacovigilance Department.

All patients who become pregnant during participation in this study are to be withdrawn from the study.

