3.2 Study Duration

It is estimated that the first patient will be enrolled in January 2020 and the last patient visit will occur approximately March 2025. The duration of study participation for each patient, in general, includes the following segments:

- **Screening Period:** up to 30 days
- **Treatment Period:** 28 days per cycle for up to 24 months of treatment or until disease progression, death, intolerable adverse events (AEs), or other protocol-specified reason for patient withdrawal
- **Safety Follow-up Visit:** 35 (± 5) days after the last dose of pozotinib
- **Long-Term Follow-up:** After study drug discontinuation, patients who have consented will be contacted every 3 months, for up to 2 years after patient's first dose of pozotinib, for survival assessment

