9. Patient is willing to practice 2 forms of contraception, one of which must be a barrier method. Female patients of childbearing potential must use an effective method of birth control (e.g., oral contraceptive, intrauterine device, bilateral tubal ligation/occlusion, condoms, or diaphragm, not engaging in sexual intercourse) during treatment period and 3 months thereafter. Males must use an effective method of birth control (e.g., condoms, vasectomy, not engaging in sexual intercourse) during treatment period and 3 months thereafter.
10. Females of childbearing potential must have a negative pregnancy test within 7 days prior to Day 1. Females who are postmenopausal for at least 1 year (defined as more than 12 months since last menses) with no other medical reasons or who are surgically sterilized do not require this test.

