5.3.9 Long-Term Follow-up – Every 3 Months

- After study drug discontinuation, patients will be contacted every 3 months, for up to 2 years after patient's first dose of pozotinib, for survival assessment.

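### Pregnancy reporting stops 35 (±5) days after the last dose although contraception is required for 3 months, leaving about 60% of the post-treatment contraception period without a reporting duty

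*Combined protocol and SAP*

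**What the plan says.** **Reporting window.** Section 7.8 covers pregnancies in a patient or a patient's "partner that occur from the first dose of study treatment through 35" (±5) days after the last dose. These go to the sponsor within 24 hours of the investigator learning of them and are followed to outcome.

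**Contraception period.** Inclusion criterion 9 (Section 4.1, and likewise the synopsis) requires women of childbearing potential to use effective contraception "during treatment period and 3 months thereafter. Males must use an effective method of birth control", and the requirement for men has the same length.

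**What else operates after the cut-off.**
- Section 7.7.1 keeps one late route open, for SAEs that arise after 35 (±5) "days after the last dose of study treatment where a causal relationship with the study drug is suspected are to be reported". Section 7.7 lists "Results in a congenital anomaly/birth defect" among the SAE criteria. Pregnancy itself is not on that list.
- The last scheduled pregnancy test is at the Safety Follow-up Visit (Sections 5.3.8 and 5.4.9). Section 4.3 allows that visit to come sooner if a new treatment is about to start.
- Under Section 5.3.9, "patients will be contacted every 3 months, for up to 2 years after patient's first dose of pozotinib, for survival assessment". No pregnancy question is listed. Sections 3.2 and 4.3 limit this contact to patients who have consented to it.

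**The concern.** The protocol asks patients to avoid conception for 3 months after treatment, but it stops requiring sites to report contraceptive failures little more than a third of the way through that time. Followed exactly, the rule places no reporting duty on a pregnancy that begins on Day 60 after the last dose. The duty to follow a pregnancy to outcome sits in the same paragraph of Section 7.8, so it does not clearly apply to that case either.

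What is at stake is safety information. Section 7.8 acknowledges that effects on fertility and fetal development have not been studied in pregnant women. Section 1.1.2.6 describes fewer viable fetuses in animals at high doses, with more resorptions and losses after implantation, though no teratogenicity in rat or rabbit. Human cases will be few, so each one that goes unrecorded is a loss of information. The point has no bearing on the efficacy analysis, the sample size or the precision of the ORR estimate.

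**Working it through.** The documents give no derived figure on this point, so there is nothing to reproduce. The check compares the two durations and then looks for any other clause that closes the gap.

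**Inputs**
- R, the reporting cut-off after the last dose: 35 days, or 30 to 40 with the tolerance (Section 7.8).
- C, the contraception period after treatment: 3 months (criterion 9). The protocol does not convert this to days. I take 91, and also try 84 (12 weeks), 90 and 92.
- T, time on treatment: the treatment period is "28 days per cycle for up to 24 months of treatment or until disease progression" or another listed reason to stop (Section 3.2). It matters only if treatment time is counted in the denominator.

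**Share of the post-treatment contraception period with no reporting duty, (C − R)/C**

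| C (days) | R = 40 | R = 35 | R = 30 |
|---|---|---|---|
| 84 | 44/84 = 52.4% | 49/84 = 58.3% | 54/84 = 64.3% |
| 90 | 50/90 = 55.6% | 55/90 = 61.1% | 60/90 = 66.7% |
| 91 | 51/91 = 56.0% | 56/91 = 61.5% | 61/91 = 67.0% |
| 92 | 52/92 = 56.5% | 57/92 = 62.0% | 62/92 = 67.4% |

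At C = 91 and R = 35 the gap is Days 36 to 91. Across every reading in the table the share runs from 52% to 67%.

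**Share of the whole contraception period, treatment included, (C − R)/(T + C), with C = 91 and R = 35**
- T = 28 days: 56/119 = 47%.
- T = 84 days: 56/175 = 32%.
- T = 24 months (730 days): 56/821 = 7%.

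**Does another clause close the gap?**
- *Late SAE route (Sections 7.7 and 7.7.1).* In part. It reaches an outcome that is serious and suspected to be drug-related. An uneventful pregnancy, or a loss not judged both serious and related, has no required route.
- *Scheduled testing.* No. The last test falls at or before the reporting cut-off.
- *Long-term follow-up.* No, as written. It collects survival only. It also ends 2 years after the first dose, while treatment may itself last 24 months. A patient treated for the full 24 months may have no such contact afterwards, and for anyone treated beyond about 21 months (24 − 3) it ends before the 3 months are over.

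**The case against.** **The two windows need not be equal.** A precautionary instruction to patients and a reporting duty on sites can differ without contradiction. The 35 (±5) days match the AE and SAE collection window (Sections 7.2, 7.3.1 and 7.7.1) and the last scheduled pregnancy test, and the breastfeeding restriction runs for 30 days after the last dose (exclusion criterion 18). This stands as an explanation of where the 35 days probably came from. The protocol does not offer it as a reason, and it does not explain why failures within the required contraception period should go uncollected.

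**A reader might infer that 60% of the protocol's own risk window goes unreported.** The documents do not support that, for three reasons. Criterion 9 covers treatment as well as the 3 months after it, and treatment time is fully covered by Section 7.8, so the share of the whole period is smaller and falls to about 7% at 24 months. The protocol never calls the 3 months a period of fetal risk or says why that length was chosen. And the absence of a duty to report does not prevent a site from reporting voluntarily.

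**Serious outcomes stay reportable.** This is correct for SAEs with suspected causality, and treatment-related SAEs are then followed under Section 7.7.1. The route is narrower than pregnancy reporting. It depends on someone learning of the outcome and suspecting the drug, after contact about pregnancy has ended.

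**The animal findings are mostly reassuring.** Section 1.1.2.6 describes embryo-fetal effects as limited and confined to high doses, without teratogenicity, and the genotoxicity tests were negative. This lowers the stakes but does not remove them, because fetal losses did occur at high dose.

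**Calendar days are not cases.** This stands. The trial has about 76 patients with previously treated advanced lung cancer who agree to contraception. The documents do not say how many have reproductive potential, and no number of missed pregnancies can be derived.

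**Conclusion.** The mismatch is real and no other clause resolves it. About 60% of the post-treatment contraception period (56% to 67% across the ±5-day tolerance at 91 days) carries no requirement to report a pregnancy or follow its outcome. The only exception is a serious outcome with suspected causality.

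This rests on two assumptions: 3 months is about 91 days, and a pregnancy counts as occurring when it begins. The percentage describes days without a duty. It is not a proportion of pregnancies missed, nor of the full contraception period including treatment.

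The sponsor should correct this as a safety-reporting matter. It takes no position on what the contraception duration ought to be.

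**What to change.** 1. Reconcile Section 7.8 with criterion 9 so that pregnancy reporting and outcome follow-up, for patients and partners, run to the end of the contraception period the protocol itself states (as now written, 3 months after the last dose). If the sponsor means the two to differ, the protocol should give the reason.
2. Instruct patients to tell the site of any pregnancy, their own or a partner's, in that period.
3. Ask about pregnancy at a contact about 3 months after the last dose. The long-term follow-up contact can serve where there is one. A single separate telephone query is needed for patients who did not consent to long-term follow-up or whose limit of 2 years from first dose has passed. Without it, the longest-treated patients would be missed.

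**Cost.** A change of wording in Section 7.8, a line in the patient instructions and the follow-up schedule, slightly longer pharmacovigilance tracking, and one extra call for some patients. The yield in cases is likely to be small.
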